7.6. Participant Characteristics

Baseline characteristics will be summarized for the ITT and per-protocol populations by treatment group and overall. Summaries will include descriptive statistics for continuous and categorical measures. Fisher's exact test or Pearson's chi-square test will be used for treatment-group comparisons of categorical data. For continuous data, analysis of variance (ANOVA), with independent factor for treatment will be used. Participant characteristics to be presented include:

- age
- gender
- race
- height
- body weight
- body mass index (weight (kg) / [height (m)]²)
- tobacco use
- alcohol use
- caffeine use

- years of education
- work status
- Baseline score as measured by PACC, ADL Prevention Questionnaire, CFI, CDR-SB, C3, MMSE, RUI-B.
- APOE4 carrier status (carrier [$\epsilon 2/\epsilon 4$, $\epsilon 3/\epsilon 4$, $\epsilon 4/\epsilon 4$], noncarrier [$\epsilon 3/\epsilon 3$, $\epsilon 2/\epsilon 2$, $\epsilon 3/\epsilon 2$]), and
- APOE4 genotype ($\epsilon 2/\epsilon 4$, $\epsilon 3/\epsilon 4$, $\epsilon 4/\epsilon 4$, no $\epsilon 4$), and
- Baseline Amyloid Centiloids

7.7. Participant Disposition

The following analyses of participant disposition will be conducted for the ITT population

- The percentage of participants discontinuing from each treatment group will be compared between groups using Fisher's exact test.
- The median time to discontinuation will also be compared between treatment groups using the Kaplan-Meier product limit estimator.

Comparisons using Fisher's exact test will be done for the overall percentage of participants who discontinue and also for each specific reason for discontinuation collected in the CRF. For any-cause discontinuation as well as discontinuation due to adverse event (AE) or death, comparisons of time-to-discontinuation will be conducted using the Kaplan-Meier product limit estimator and the associated log-rank test. For any-cause discontinuation, for participants who discontinue, time to discontinuation will be defined as the date of study disposition minus randomization date. For participants who did not discontinue, they will be considered censored and time will be defined as completion date of the double-blind period minus randomization date. For discontinuation due to adverse event or death, for participants who discontinue due to one of those reasons, time to discontinuation will be defined as the date of study disposition minus randomization date. All other participants will be considered censored and time will be defined as either completion date of the double-blind period minus randomization date or study disposition date (but not for AE or death) minus randomization date.

7.8. Concomitant Medications

Prior medications are defined as those that stop before randomization (Visit 6). Concomitant medications are defined as those being taken on or after randomization (Visit 6). A summary of concomitant medications will be presented as frequencies and percentages for each treatment group. Fisher's exact test will be used to test for treatment differences between groups.

If the start or stop dates of medications are missing or partial to the degree that determination cannot be made of whether the medication is prior or concomitant, the medication will be deemed concomitant. Medications will be coded using the World Health Organization (WHO) drug dictionary.

7.9. Efficacy Analyses

7.9.1. Analysis of Primary Outcome (Placebo-Controlled Period)

7.9.1.1. NCS Analysis of Primary Outcome

The primary objective of this study is to test the hypothesis that intravenous infusion of solanezumab will slow cognitive decline in preclinical AD as compared with placebo.

The original mITT analysis (that is, all participants as randomized to treatment who have a baseline and at least 1 postbaseline measure) for the primary outcome will be retained and conducted at the end of the treatment period, although the dose was increased during the study and dosing and assessments were interrupted due to COVID-19; in other words, the primary analysis will include all data for the solanezumab group as the treatment group versus placebo. As with the original analysis plan, the hypothesis for this analysis will be tested against a two-sided alpha level of .05.

The details of this analysis including the analytic method and model are presented below.

An NCS analysis with 2 degrees of freedom will be used to assess the difference between treatment groups in change from baseline for the PACC score at 240 weeks. The composite score at baseline and each post-baseline visit will be the dependent variable. Time will be treated as a continuous variable with values equal to the years between baseline and follow-up exam dates. We will assume an unstructured covariance structure, where the time values are mapped back to the corresponding visits. The NCS basis expansion will assume an interior knot at the median of observation times, and boundary knots at zero years and the maximum follow-up (Hastie 1992). The fixed effects will include the following terms: (i) NCS basis expansion terms (two terms), (ii) NCS basis expansion terms-by-treatment interaction (two terms), (iii) PACC test version administered, (iv) age, (v) education, (vi) APOE4 Carrier Status (yes/no), and (vii) baseline florbetapir cortical SUVr. The model is constrained to not allow a difference between treatment group means at baseline.

The null hypothesis is that the treatment difference between solanezumab and placebo for the PACC score at 240 weeks is equal to zero. The primary analysis will be carried out in the mITT population that is randomized and has a baseline score and at least 1 post-baseline assessment. If the unstructured covariance structure matrix results in a lack of convergence, the following structures will be used in sequence:

- heterogeneous Toeplitz covariance structure
- heterogeneous autoregressive order 1 covariance structure
- heterogeneous compound symmetry covariance structure, and
- compound symmetry covariance structure.

The Satterthwaite approximation will be used to estimate the denominator degrees of freedom. The model with unstructured covariance structure will be fit in R using the `lme4::lmer` function.

Other correlation structures will be fit with the nlme::gls function. The emmeans R package will be used to calculate the Satterthwaite approximation for denominator degrees of freedom.

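### If the primary PACC model falls back to a simpler covariance, the SAP names no robust standard error, so the 5% level is not protected at that step

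*SAP*

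**What the plan says.** SAP 7.9.1.1 analyses PACC with a constrained natural cubic spline (NCS) model, and "the hypothesis for this analysis will be tested against a two-sided alpha level of .05". On the covariance it says: "We will assume an unstructured covariance structure, where the time values are mapped back to the corresponding visits". The contingency reads "If the unstructured covariance structure matrix results in a lack of convergence, the following structures will be used in sequence", followed by heterogeneous Toeplitz, heterogeneous AR(1), heterogeneous CS and CS. Protocol 11.2.8 has the same sequence, and SAP 7.1 extends it to the NCS and MMRM analyses generally.

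On inference the section says only "The Satterthwaite approximation will be used to estimate the denominator degrees of freedom". On software it says "The model with unstructured covariance structure will be fit in R using the `lme4::lmer` function", and it assigns the other structures to nlme::gls. Neither document names a robust or sandwich variance, so model-based standard errors are the natural reading, by omission rather than by statement. Neither document says what counts as lack of convergence.

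**The concern.** Satterthwaite's method changes the reference degrees of freedom, not the variance estimator. With an unstructured covariance the model-based standard error (SE) is right in large samples. With a restricted structure it is right only if that structure holds, and otherwise the Week 240 test can be anti-conservative or inefficient.

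The planning figures suggest that a restricted structure may not hold. The SDs in SAP 6.2 rise from 2.85 at Week 240 to 3.77 at Week 336 (ADNI), and from 3.08 to 3.99 (HABS). That is what participants declining at different rates would produce. In such data the correlation between two visits depends on when they occur as well as how far apart they are, which none of the four fallbacks allows.

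The software choice raises a second question. lmer has no residual correlation structure, so an unstructured covariance has to be emulated with one random effect per visit. A fallback might then be triggered by the parameterisation rather than by the data. At stake is the error rate, or the power, of the trial's only confirmatory p-value.

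**Working it through.** **Inputs from the documents.** N = 1150, 1:1; 30% attrition; SD 2.85 (ADNI) or 3.08 (HABS) at Week 240 and 3.77 or 3.99 at Week 336; visit-to-visit correlation about 0.5, stated for the open-label calculation (SAP 6.2; Protocol 11.1). PACC is scheduled at 11 visits, Weeks 0 to 240 (Protocol Attachment 1). The spline has 2 df (SAP 7.9.1.1).

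**Assumptions.** The true covariance, the baseline SD, the residual SD and the monotone dropout pattern are not in the documents. The Week 336 SDs are read as SDs of change.

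**1. Reproducing the planned power.** Completers only, 575 × 0.70 = 402.5 per arm: 0.532 / (2.85 × √(2/402.5)) = 2.648, so power is Φ(2.648 − 1.96) = 75.4% (HABS 74.7%). Both are below the stated 80%. An MMRM information formula with 10 post-baseline visits, retention falling linearly to 70% and constant correlation 0.5 has variance factor 1.256. The effective n is 575/1.256 = 457.8 per arm, and power is 80.6% (ADNI) and 80.0% (HABS). The detectable differences are 0.528 and 0.570, against the stated 0.532 and 0.570. The planned power is therefore reproduced under constant correlation 0.5.

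**2. Calibrating a random slope to the stated SDs.** With t in years (240/52.1775 = 4.600; 336/52.1775 = 6.440), the variance of change is s²t² + 2σ².
- ADNI: s² = (3.77² − 2.85²)/(6.440² − 4.600²) = 6.090/20.31 = 0.300, so s = 0.548. σ² = (8.1225 − 0.300 × 21.16)/2 = 0.889, so σ = 0.943.
- HABS: s = 0.563 and σ = 1.180 by the same steps.

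**3. Type I error at each fallback.** For a true covariance V, take the working covariance W of each structure that maximises the expected Gaussian likelihood over the dropout patterns. With A = ΣX′W⁻¹X:
- model variance = A⁻¹
- true variance = A⁻¹(ΣX′W⁻¹VW⁻¹X)A⁻¹
- type I error = 2 × [1 − Φ(1.96 × SE_model/SE_true)]

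| Assumed true covariance | Het. Toeplitz | Het. AR(1) | Het. CS | CS |
|---|---|---|---|---|
| Constant SD, constant correlation 0.5 | 5.0% | 3.4% | 5.0% | 5.0% |
| Random intercept and slope; change SD 2.85 or 3.08, residual SD 1.0–1.9, baseline SD 2.2–2.7 | 5.4–8.5% | 3.9–6.3% | 7–33% | 8–40% |
| Random slope as in step 2; baseline SD 2.0–3.2 | 5.9–9.1% | 2.6–7.0% | 24–35% | 33–40% |
| AR(1), 0.5 per visit | 5.0% | 5.0% | 16.4% | 16.8% |

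One case from the second row (change SD 2.85, residual SD 1.3, baseline SD 2.7) gives 6.6%, 4.5%, 22.4% and 27.4%. Inverting the formula, SE_model/SE_true is 0.94, 1.02, 0.62 and 0.56. In this case, moving the spline boundary knot from 4.65 to 7 years or dropout from 0 to 40% changes the results by about 1 percentage point or less.

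**4. Efficiency at AR(1).** Under random-slope covariances the true SE at AR(1) is roughly 15–40% above unstructured. If the unstructured test has 80% power, its noncentrality is 1.960 + 0.842 = 2.802. Power then falls to Φ(2.802/1.15 − 1.96) = 68%, or Φ(2.802/1.40 − 1.96) = 52%.

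**5. Does a sandwich SE repair the size?** Monte Carlo for the single case in step 3, with 1500 trials and the working covariance held at its best-fitting value:

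| | Het. Toeplitz | Het. CS | CS |
|---|---|---|---|
| Model-based SE | 6.3% | 22.4% | 27.3% |
| Participant-clustered sandwich SE | 5.0% | 5.5% | 5.4% |

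The Monte Carlo error at 5% is √(0.05 × 0.95/1500) = 0.6 percentage points.

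**6. The lmer parameterisation.** Eleven visit effects per participant make 1150 × 11 = 12,650 random effects. With linear attrition to 30%, the observations number 1150 × (1 + Σ(1 − 0.03k), k = 1 to 10) = 1150 × 9.35 ≈ 10,750. The marginal covariance is G + σ²I. Any σ² below the smallest eigenvalue of V, with G adjusted to match, gives the same V, so σ² is not identified.

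**The case against.** The strongest reply is that this is a contingency. The planned test is unstructured and its level is not in question. The CS figures need at least three successive failures (unstructured, Toeplitz, AR(1)), and heterogeneous AR(1) has only 12 covariance parameters for about 1,150 participants. That stands.

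A reader might infer four stronger things that the documents do not support:

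- **That the trial's type I error is inflated to a particular percentage.** No PACC covariance is given. The one stated correlation, about 0.5, reproduces the planned power when held constant, and then gives 5.0% at three of the four fallbacks. Constant SD sits poorly with the rise in SD between Weeks 240 and 336, but that rise makes a random slope plausible without establishing it.
- **That growing spread alone defeats every fallback.** The three heterogeneous structures allow visit-specific variances. Rising SDs with constant correlation are fitted exactly by heterogeneous CS and heterogeneous Toeplitz. The inflation needs the further assumption that correlation changes with time.
- **That error grows steadily down the list.** AR(1), the second step, is near nominal or conservative in every case examined; what it loses is power.
- **That a fallback is likely.** No lmer fit was run. The redundancy in step 6 leaves V, the estimate and its SE unchanged if the fit completes, and a count of random effects is not evidence of non-convergence. Nor is it shown that gls converges more readily.

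Prespecifying an order of structures is also good practice, because it limits analyst discretion. What it leaves open is how the SE is computed once the order is used.

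**Conclusion.** The point holds as a conditional one. If the unstructured fit fails, the rule as written gives a primary p-value whose error rate depends on an unverified covariance structure:

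- **Heterogeneous Toeplitz:** 5% under constant correlation 0.5; about 5–9% under random-slope covariances consistent with the stated SDs.
- **Heterogeneous AR(1):** about 3–7%, with a true SE roughly 15–40% above unstructured.
- **The two CS steps:** 5% under constant correlation 0.5 and constant SD; about 7–40% under the random-slope covariances.

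These are large-sample figures. They rest on assumed covariances and baseline SDs, planning attrition of 30% and monotone dropout. Each applies only if its step is reached, and the unstructured analysis keeps its 5% level. The probability of reaching any step is unknown. This is a should-fix, not a defect in the planned primary test.

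**What to change.** In SAP 7.9.1.1, and by the same rule in SAP 7.1 for the other NCS and MMRM analyses:

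1. If any fallback structure is used, base the Week 240 test and 95% confidence interval on a participant-clustered sandwich SE with a small-sample correction.
2. Fit the unstructured model in nlme::gls (corSymm with varIdent by visit), which the SAP already names for the other structures, and judge convergence on that fit. A fallback could then not come from the unidentified residual variance in an lmer emulation.

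The cost is two SAP sentences and a few lines of code, and the change should be made before unblinding so that the variance estimator is not chosen with results in view. A sandwich SE is slightly more variable, which is minor at about 1,150 participants. It corrects the variance only. It does not recover lost efficiency, and it does not remove bias from outcome-dependent dropout under a misspecified covariance. Those limits are a further reason to avoid an unnecessary fallback.

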7.9.1.2. Sensitivity Analyses

7.9.1.2.1. MMRM Analysis of Primary Outcome

An MMRM analysis will be used to assess the difference between treatment groups in change from baseline for the PACC score at 240 weeks (Visit 66). Change from baseline at each visit when the composite score is scheduled will be the dependent variable. Visit will be treated as a categorical variable with values equal to the visit numbers at which the composite measure was scheduled. We will assume an unstructured covariance structure. The model for the fixed effects will include the following terms: (i) baseline PACC score, (ii) treatment, (iii) visit, (iv) treatment-by-visit interaction, (v) age, (vi) education, (vii) APOE4 Carrier Status (yes/no), and (viii) baseline florbetapir cortical SUVr.

The null hypothesis is that the treatment difference between solanezumab and placebo for the PACC score at 240 weeks is equal to zero. The primary analysis will be carried out in the mITT population that is randomized and has a baseline score and at least 1 post-baseline assessment. If the unstructured covariance structure matrix results in a lack of convergence, the same sequence of covariance structures as above will be attempted. Additionally, a Bayesian disease progression model (DPM) (Sparks 2021) with a proportional treatment effect will be conducted to assess statistical differences in the rate of decline of the PACC score between the solanezumab group and the placebo group. The analysis is testing the hypothesis that the disease progression ratio (DPR), defined as the ratio of the rate of decline of the solanezumab arm divided by the rate of decline of the placebo arm, is less than 1.

$$H_0: DPR=1$$

$$H_1: DPR<1$$

The key assumption of the DPM is that it assumes that the treatment effect of solanezumab is proportional to placebo over the course of the study. The proportionality assumption is similar to the assumption made in proportional hazards modeling of time to event data. The model includes diffuse priors on all parameters; therefore, the prior distributions have very little impact on the posterior distributions. No information or knowledge of the effect of solanezumab from previous studies will be incorporated into the prior distributions.

The DPM is as follows:

$$Y_{ij} = \gamma_i + e^{\theta T_i} \sum_{v=0}^j \alpha_v + \varepsilon_{ij}$$

where Y_{ij} denotes the PACC score at visit j for participant i ; the PACC score for a participant at baseline (prior to treatment) is Y_{i0} . The value γ_i ($i=1, 2, \dots, k$) represents a participant specific random effect. The parameter T_i denotes the treatment arm for participant i , where T_i has a value

of 1 if a participant is randomized to solanezumab, and a value of 0 if the participant is randomized to placebo. The parameter α_v is the change in mean PACC score for placebo from visit $v-1$ to v , and ε_{ij} is the error term. The DPR for solanezumab relative to placebo is provided by the parameter e^θ . Covariates of the model include PACC test version, age at baseline, education, APOE4 Carrier Status (yes/no), and baseline florbetapir cortical SUV_r.

To examine the hypothesis of a disease progression benefit, we calculate the posterior probability of the alternative hypothesis for various thresholds (for example, 0% slowing, 25% slowing relative to placebo, etc.). A 95% credible interval (from the 2.5th to the 97.5th percentiles) and posterior mean and median disease progression ratio will be presented.

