11.1. Determination of Sample Size

In order to develop an appropriate measure of cognitive decline in a preclinical population, we tested several combinations of measures using data from longitudinal studies in clinically normal populations, including the ADNI; the AIBL; the ADCS-PI trial; and the HABS ([Attachment 3](#)).

Sample size and power at 4.5 years (240 weeks) for the PACC were estimated using data from ADNI and HABS. Estimates were obtained by applying appropriate assumptions regarding treatment difference, SD, and attrition for a 4.5-year study in a preclinical AD population. In ADNI, the difference in the composite change between subjects with and without elevated brain amyloid at 240 weeks was 2.13 (SD=2.85). Similarly, in HABS, the difference in the composite change between subjects with and without elevated brain amyloid at 240 weeks was 2.66 (SD=3.08). Given the ADNI-derived estimate of SD at 240 weeks of SD=2.85 and 30% attrition, the total N=1150 provides 80% power (5% 2-sided alpha) to detect a treatment difference of 0.532 points or $0.532/2.13 = 24.9\%$ of the amyloid group difference. Similarly, based on the HABS estimate of SD at 240 weeks of SD=3.08, the study has 80% power to detect a treatment difference of 0.570 points or $0.570/2.66 = 21.4\%$ of the amyloid group difference.

For the open-label period, the estimated mean PACC difference between cognitively normal subjects with and without elevated brain amyloid at 336 weeks is 2.95 (SD=3.77) based on ADNI and 4.74 (SD=3.99) based on HABS. Accounting for the administrative censoring that will be induced by the common close design of the open-label period, and assuming an overall attrition rate of 30%, about 266 PACCs are expected to be available at 336 weeks. The visit-to-visit correlation is estimated to be about 0.5. Under these pilot estimates, 266 PACCs at 336 weeks would provide 80% power to detect a randomized group (early-start vs delayed-start treatment with solanezumab) difference of about 0.9 PACC points. This change of 0.9 PACC points reflects 30% of the difference between amyloid-positive and -negative participants based on ADNI, and 20% of that difference based on HABS.

Sample size for the study was determined prior to the interruption caused by the COVID-19 pandemic. Applying the NCS approach in simulated trials with a COVID-19 pandemic interruption suggests the study has 94% power to detect an effect size of 0.75 PACC points at 240 weeks.

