6.1. Summary of Study Design

Study A4 is a multicenter, randomized, double-blind, placebo-controlled, Phase 3 study comparing solanezumab with placebo for 240 weeks in approximately 1150 participants ages 65 to 85 years old with preclinical AD, defined as having evidence of brain amyloid pathology without clinically evident cognitive impairment at screening. Participants who met entry criteria were randomized in a 1:1 ratio (approximately 575 per treatment arm) to solanezumab or placebo once every 4 weeks. Participants were randomized within the site by education – high (13 or more years) or low (12 or less years) and the presence of one or more apolipoprotein E gene (APOE) ϵ 4 alleles (yes, no). The primary hypothesis being tested is that the cognitive decline at the end of the placebo-controlled period will be significantly less for solanezumab than for placebo. Participants completing the placebo-controlled period of the study can opt to participate in the open-label period of the study that will last for up to 204 weeks or until the primary analyses of the placebo-controlled period of the study are completed and reviewed.

At the beginning of the COVID-19 pandemic, a hiatus was implemented to allow participants to pause study activities without missing visits and resume when COVID safety mitigations were in place (for example, vaccines, home infusions, etc.). The hiatus extended the end of the placebo-controlled period for up to 9 months and the placebo-controlled period will be administratively closed in December 2022.

Figure A4.SAP.1 illustrates the study design.

Abbreviation: V = visit.

Figure A4.SAP.1. Illustration of study design for Clinical Protocol A4.

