6.2. Determination of Sample Size

In order to develop an appropriate measure of cognitive decline in a preclinical population, we tested several combinations of measures using data from longitudinal studies in clinically normal populations, including the ADNI; the AIBL; the ADCS-PI trial; and the HABS.

Sample size and power at 4.5 years (240 weeks) for the PACC were estimated using data from ADNI and HABS. Estimates were obtained by applying appropriate assumptions regarding treatment difference, SD, and attrition for a 4.5-year study in a preclinical AD population. In ADNI, the difference in the composite change between participants with and without elevated brain amyloid at 240 weeks was 2.13 (SD=2.85). Similarly, in HABS, the difference in the composite change between participants with and without elevated brain amyloid at 240 weeks was 2.66 (SD=3.08). Given the ADNI-derived estimate of SD at 240 weeks of SD=2.85 and 30% attrition, the total N=1150 provides 80% power (5% 2-sided alpha) to detect a treatment difference of 0.532 points or $0.532/2.13 = 24.9\%$ of the amyloid group difference. Similarly, based on the HABS estimate of SD at 240 weeks of SD=3.08, the study has 80% power to detect a treatment difference of 0.570 points or $0.570/2.66 = 21.4\%$ of the amyloid group difference.

For the open-label period, the estimated mean PACC difference between cognitively normal participants with and without elevated brain amyloid at 336 weeks is 2.95 (SD=3.77) based on ADNI and 4.74 (SD=3.99) based on HABS. Accounting for the administrative censoring that will be induced by the common close design of the open-label period, and assuming an overall attrition rate of 30%, about 266 PACCs are expected to be available at 336 weeks. The visit-to-visit correlation is estimated to be about 0.5. Under these pilot estimates, 266 PACCs at 336 weeks would provide 80% power to detect a randomized group (early-start vs delayed-start treatment with solanezumab) difference of about 0.9 PACC points. This change of 0.9 PACC points reflects 30% of the difference between amyloid-positive and -negative participants based on ADNI, and 20% of that difference based on HABS.

Sample size for the study was determined assuming an MMRM analysis prior to the interruption caused by the COVID-19 pandemic. Applying the NCS approach in simulated trials with a COVID-19 pandemic interruption suggests the study has 94% power to detect an effect size of 0.75 PACC points at 240 weeks.

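### As written, the Bayesian disease progression model has no term for people declining at different rates; if errors are independent and the SD of PACC change grows as in the planning cohorts, its 95% credible interval covers about 61–83%

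*SAP*

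**What the plan says.** SAP 7.9.1.2.1 adds a Bayesian DPM to the sensitivity analyses of the PACC. The score of participant i at visit j is a participant effect, plus exp(θ × treatment) times the cumulative sum of the placebo visit-to-visit changes α_v, plus ε_ij. The progression ratio (DPR) is exp(θ).

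- The participant effect γ_i "represents a participant specific random effect". It carries no visit index and no time multiplier.
- ε_ij "is the error term". No distribution, variance or within-person correlation is given.
- On priors: "The model includes diffuse priors on all parameters". The SAP adds that they have very little influence on the posterior.
- The output is the posterior probability of benefit at several degrees of slowing (0% and 25% are the examples), with a 95% credible interval. The "posterior mean and median disease progression ratio will be presented".

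The SAP names an unstructured covariance for the NCS and MMRM analyses (7.1, 7.9.1.1 and the MMRM text of 7.9.1.2.1). It names none for the DPM.

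Protocol 11.1 and SAP 6.2 give an SD of PACC change at week 240 of 2.85 (ADNI) and 3.08 (HABS). For week 336 the protocol says that "the estimated mean PACC difference between cognitively normal subjects with and without elevated brain amyloid at 336 weeks is 2.95 (SD=3.77) based on ADNI"; the HABS SD there is 3.99. The same paragraph puts the visit-to-visit correlation at about 0.5.

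**The concern.** A random intercept with independent, equal-variance errors is compound symmetry, which SAP 7.9.1.1 lists as the last fallback for the primary model. Under it, the variance of change from baseline is the same at every visit. The planning figures contradict this. From week 240 to week 336 the variance of change rises by 3.77²/2.85² = 1.75 (ADNI) and 3.99²/3.08² = 1.68 (HABS), while follow-up time rises by 336/240 = 1.4. The variance grows faster than time, and most of the way to the 1.4² = 1.96 of a pure random slope.

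If people decline at different rates, one person's late deviations go together. A model without a term for that counts them as separate pieces of information, so the credible interval is too narrow and the posterior probabilities of slowing are too close to 0 or 1. Because the priors are diffuse, nothing offsets this.

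**Working it through.** **Inputs from the documents.** SDs of 2.85 and 3.77 (ADNI), 3.08 and 3.99 (HABS); correlation 0.5; 575 per arm; 30% attrition (Protocol 11.1, SAP 6.1 and 6.2); PACC every 24 weeks from week 0 to 240 (Protocol Attachment 1).

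**Assumptions.** The week-336 SDs are SDs of change. Errors are independent with equal variance. Attrition is linear over visits. Placebo decline at week 240 equals the amyloid-group difference (2.13 ADNI, 2.66 HABS). Between-person baseline variance is 4 to 7.6, which barely matters.

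**Step 1: the plan's own figure.** SAP 6.2 says that "the total N=1150 provides 80% power (5% 2-sided alpha) to detect a treatment difference of 0.532 points".
- Completers only, 0.7 × 575 = 402.5 per arm: 2.80 × 2.85 × √(2/402.5) = 0.563, which does not reproduce it.
- Repeated measures with constant SD, correlation 0.5, 10 post-baseline visits and linear attrition to 30%: 0.530 (ADNI) and 0.573 (HABS), against the stated 0.532 and 0.570. This reproduces it, so the 0.5 cannot be set aside.

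**Step 2: variance components if all SD growth is a random slope.** With time in years (240 weeks = 4.60, 336 weeks = 6.44), SD² = 2σ²_e + σ²_slope × t².
- ADNI: σ²_slope = (3.77² − 2.85²)/(6.44² − 4.60²) = 6.09/20.3 = 0.300; σ²_e = (8.12 − 0.300 × 21.2)/2 = 0.89.
- HABS: σ²_slope = 6.43/20.3 = 0.317; σ²_e = 1.39.

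**Step 3: coverage.** The best-fitting random-intercept model is found. Its model-based SE for θ is then compared with the true (sandwich) SE. Coverage = 2Φ(1.96 × SE_model/SE_true) − 1. With DPR = 1, the chance that the posterior probability of benefit exceeds 0.975 is 1 − Φ(1.96 × SE_model/SE_true).

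Under the random slope, SE_model/SE_true is 0.437 to 0.495:
- 1.96 × 0.437 = 0.857, so coverage is 0.609 and the tail is 0.196.
- 1.96 × 0.495 = 0.970, so coverage is 0.668 and the tail is 0.166.

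| True covariance | Cohort | SE_true/SE_model | Coverage | Pr(posterior > 0.975), DPR = 1 |
|---|---|---|---|---|
| Random slope | ADNI | 2.2–2.3 | 61–62.5% | 19–20% |
| Random slope | HABS | 2.0–2.1 | 65–67% | about 17% |
| Same SD growth, correlation 0.5 for all pairs | ADNI | 1.52 | 80% | 9.9% |
| Same SD growth, correlation 0.5 for all pairs | HABS | 1.45 | 82.5% | 8.8% |
| Same SD growth, 0.5 for adjacent visits, decaying | ADNI | 1.57 | 79% | 10.6% |
| Same SD growth, 0.5 for adjacent visits, decaying | HABS | 1.53 | 80% | 10.0% |
| Constant SD, correlation 0.5 | ADNI | 1.00 | 95% | 2.5% |

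**Step 4: simulation.** With 1,500 trials per scenario and the random slope as truth, coverage was 62.1% and 61.8% (ADNI, DPR 1 and 0.75) and 66.1% and 66.9% (HABS). A 400-trial run with a full posterior for θ (ADNI, DPR = 1) gave 66.0%, Monte Carlo SE 2.4 points. With constant SD, simulated coverage was 94.9%.

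**Step 5: after the fix.** With a random slope in the model, simulated coverage at DPR = 1 was 95.6% (ADNI) and 95.5% (HABS). The false-signal rate fell to about 2%. Interval width on the log-ratio scale rose from 0.141 to 0.307 (ADNI) and from 0.130 to 0.261 (HABS). The full-posterior run gave 93.8% coverage and a 5.0% false-signal rate.

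**The case against.** The best counter-argument is that independence is not in the SAP. The error term is simply undescribed, and the source cited for the model, which may define it, is not available here. A correlated or heterogeneous ε_ij would reduce or remove the problem. That stands, and it makes every coverage figure conditional. It does not rescue the text: no general rule in the SAP supplies a covariance for the DPM, and a random intercept with plain error is the ordinary reading of the formula.

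A reader might infer that coverage is simply 61–67%. The documents do not support that. The figure needs all SD growth to be a linear random slope, with two variances solved from two SDs and one of those SDs taken from beyond the 240-week period. It implies a correlation of 0.88 (ADNI) or 0.84 (HABS) between the changes at weeks 216 and 240, against the stated 0.5. Applied to the power calculation, that covariance gives 0.511 and 0.556, a poorer match than correlation 0.5. Applying 0.5 with the same SD growth gives 79–83%. Only a constant SD gives 95%, and that contradicts the growing SDs in the same section.

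Nor is the 9–20% a trial error rate. The SAP sets no 0.975 cut-off for the DPM, and SAP 7.4 makes every other analysis secondary to the NCS analysis. A reader might also suppose that the DPM would be the result most quoted as percent slowing; nothing in the documents says so.

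**Conclusion.** The point holds as a defect in a sensitivity analysis. The formula has no term for between-person differences in rate of decline. On every reading examined that combines independent, equal-variance errors in the model with the planning cohorts' growing SDs, the interval is materially too narrow. Coverage is about 61–83% for a nominal 95%, and the posterior probabilities of slowing are overconfident to match.

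The size depends on the unstated error covariance and on how the SD growth is split between slope and correlation, so the range should be quoted and not its lower end. A reader might extend this to the trial's main result. The documents do not support that, because the primary NCS analysis and the MMRM both specify an unstructured covariance.

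**What to change.** In SAP 7.9.1.2.1, do one of the following:

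- keep γ_i and add a participant-level random slope in time; or
- replace γ_i with an unstructured (or heterogeneous Toeplitz) within-participant residual covariance, as in the primary model. It should replace γ_i and not be added to it, because the two cannot be separated.

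State the residual covariance explicitly in either case. Check coverage and the behaviour of the posterior probabilities by simulation under the actual priors. Only the random-slope option has been tried here, and its full-posterior run (93.8% coverage, 5.0% false signals) is reason enough to check.

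A separate notation point: the sum starts at v = 0, where a change from visit v − 1 is undefined. Set α_0 = 0 (start at v = 1) so that the ratio does not multiply a baseline term. The practical effect is probably small, since SAP 5.1 centres each component on its baseline mean.

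The cost is a few lines of SAP text, a slower fit and a wider reported interval, about double on the log-ratio scale under the random-slope assumption. No new data or visits are needed.
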